10 STUDY DESIGN

This study is a prospective, multi-center, open-label, single-arm, clinical investigation to evaluate the Minitouch Endometrial Ablation System in up to 126 premenopausal women with menorrhagia. The treatment procedure may be performed in an office setting or ambulatory / outpatient surgery centers/operating room (OR).

Candidates will be identified via review of existing patient records and, if necessary, as a result of IRBapproved recruitment advertisements (see **Figure 10-1: Study Execution Diagram**). Study staff will confirm general eligibility and identify already existing SOC (standard of care) testing which may be applied to the trial.

Study staff will obtain written informed consent as outlined in Section 11.5 Informed Consent.

Screening may require more than one visit. The first visit requires documentation of written informed consent and it is recommended that the visit include patient training on the method of collecting PBLAC diary data, a validated patient self-reported menstrual diary scoring system. ⁽²⁾

A subsequent visit may occur after approximately one month, and after completion of the PBLAC diary. The subject will return the completed PBLAC diary and the site personnel will confirm menorrhagia with a PBLAC a score of \geq 150. Then the patient will continue screening for additional eligibility assessments as outlined in **Figure 10-1: Study Execution Diagram** and **Section 12.3 Screening Visits.**

Patient enrollment occurs on the day of the treatment following confirmation of eligibility. Once confirmed, then the patient may undergo the Minitouch procedure. One day after procedure, the study staff will contact the patient to assess the patient's procedure-related pelvic pain level utilizing the NRS (0-10 scale). Every effort should be made to ensure the 24-hour contact is conducted even if the window falls on a weekend. The follow-up visits will occur at 2 weeks, 3 months, 6 months and 12 months, 24 months, and 36 months post-procedure. Total study duration for a Patient is approximately 37 months, including one month of pre-enrollment assessment, and 36 months post-treatment follow up.

CONFIDENTIAL & PROPRIETARY

***NOTE:** Final eligibility must be confirmed by the investigator prior to procedure initiation.

Figure 10-1: Study Execution Diagram

Page 26 of 65

CONFIDENTIAL & PROPRIETARY

11 PATIENT ENROLLMENT AND SELECTION

11.1 Study Population

The target patient population is adult females age 30 - 50 years old that meet the eligibility criteria as outlined in **Section 11.3 Patient Selection Criteria**. All patients must sign the study-specific informed consent form and meet all inclusion criteria and have no exclusion criteria.

11.2 Prescreening

The investigators may prescreen prospective candidates prior to consent by reviewing current medical files to assess eligibility according to the selection criteria. Applicable testing or information obtained in standard of care medical visits or obtained via recruitment services may be utilized for the study if the test was completed within the validity windows.

No prospective protocol-specific testing or medication changes shall occur until the informed consent form (ICF) is signed by the patient and the delegated clinical site personnel.

11.3 Patient Selection Criteria

Patients who meet the inclusion criteria and do not fulfill any of the exclusion criteria will be eligible for participation in this study.

11.3.1 Inclusion Criteria

Patients eligible for inclusion in this study must fulfill the following criteria:

- 1) Female patient age 30 to 50 years
- 2) Excessive menstrual bleeding due to benign causes
- 3) Uterine sounding depth measurement of 6.0 12.0cm (external os to internal fundus)
- 4) A minimum uterine cavity length of 4.0cm (internal os to internal fundus)
- 5) A minimum PBLAC score of ≥ 150 for 1 menstrual cycle (obtained during screening) and must also have a documented history of excessive menstrual bleeding prior to study enrollment
- 6) Endometrial biopsy within 12 months prior to treatment procedure with no abnormal pathology
- 7) Premenopausal at screening as determined by FSH measurement \leq 40 IU/L when age is \geq 40 years
- 8) Patient agrees to use a reliable form of contraception during the study, and follows these requirements:
 - a. If a hormonal birth control method is used for contraception, the patient must have been on said method for ≥ 3 months prior to the onset of the screening menstrual cycle and agrees to remain on the same hormonal regimen through the initial 12-month follow-up (pills, injections, patches, rings, implants)
 - b. Patient also agrees to not use hormonal birth control during the first 12-month posttreatment follow-up period if they were not using hormonal birth control during the 3 months prior to treatment
- 9) Ability to provide written informed consent
- 10) Patient is literate and clearly demonstrates understanding on how to use PBLAC after training
- 11) Patient agrees to the following during the study:
 - a. No initiation of hormonal contraception or any other medical intervention for bleeding
 - b. Attend all follow-up exams and submission of completed PBLAC diaries through the 36month follow-up timepoint

c. Exclusive use of study-provided sanitary products and submission of completed PBLAC diaries through the 12-month post-treatment follow-up

11.3.2 Exclusion Criteria

Patients will be excluded from this study if they meet any of the following criteria:

Patient Conditions:

- 1) Pregnant, or desires to retain fertility
- 2) Current or documented history of endometrial hyperplasia
- 3) Active endometritis
- 4) Clinically significant or suspected adenomyosis indicated by patient complaints, imaging or clinician's judgment
- 5) Active infection of the genitals, vagina, cervix, uterus, adnexa or urinary tract
- 6) Active pelvic inflammatory disease
- 7) Currently using an intrauterine device (IUD), including Mirena[™] device, and unwilling to remove the IUD
- 8) Presence of an implantable contraceptive device (e.g., Essure[®]) protruding into the uterine cavity
- 9) Active sexually transmitted disease (STD) at the time of ablation
- 10) Presence of bacteremia, sepsis, or other active systemic infection
- 11) Currently on anticoagulants
- 12) Known clotting defects or bleeding disorders
- 13) Currently on medications that could thin the myometrial muscle, such as long-term steroid use (except inhaler or nasal therapy for asthma or other pulmonary conditions)
- 14) Previous medical/surgical treatments, or has other conditions, that could lead to anatomic/pathologic weakness or thinning of the myometrium (Classical caesarean section and transmural myomectomy are examples of such treatments that may interrupt the integrity of the uterine wall)
- 15) Any general health, mental health or social situation which, in the opinion of the investigator, could represent an increased risk for the patient, or the ability of the patient to complete study requirements.

Patient Anatomy:

- 16) Known/suspected abnormal uterine/pelvic anatomy or condition, such as frozen pelvis
- 17) Abdominal, pelvic or gynecological malignancy
- 18) Untreated/unevaluated cervical dysplasia, except cervical intraepithelial neoplasia I (CIN I)
- 19) Previous endometrial ablation procedure
- 20) Abnormal or obstructed, or perforated cavity as determined by investigator via standard clinical practices (e.g., hysteroscopy, saline infusion sonohysterography). This includes, but is not limited to:
 - a. Septate or bicornuate uterus, arcuate uterus or other congenital malformation of the uterine cavity
 - b. Pedunculated or submucosal myomas distorting the uterine cavity or not fully resected
 - c. Polyps larger than 1 cm
- 21) Intramural or subserosal myomas > 3 cm in size, or any myoma that distorts the uterine cavity

General Exclusions

22) Any patient who is currently participating or considering participation in any other research of an investigational drug or device

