12.3.3 Screen Failures

Candidates who sign an informed consent form and fail to meet the inclusion and/or exclusion `criteria or who terminate from the study prior to treatment initiation are defined as screen failures. Screen failures are excluded from participation in the study. In some cases, subjects may be rescreened (See **11.4 Rescreening**). If needed, obtain guidance from the Sponsor clinical staff to determine if a screen failed subject may be rescreened.

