12.4 Procedure (Day 0) – Enrollment / Discharge

12.4.1 Procedure Visit Strategy

On the day of procedure, first complete the reassessment of the selection criteria. This will include urine pregnancy testing, vital signs, medication review, assessment for the presence of infection or STD. If the urine pregnancy test is positive, then the patient is a screen failure.

Ensure that all existing tests remain within the validity windows.

Once the final eligibility is confirmed, the patient is enrolled and may proceed to treatment.

Prior to administration of procedure meds, have the subject complete the pelvic pain NRS prior to the procedure as a baseline. Then the pelvic pain NRS will be assessed again at discharge and as part of the SOC 24-hour follow-up phone contact.

Perform the procedure using the anesthesia of choice (as appropriate) and in accordance with the IFU.

After the procedure, assess the patient for AEs, SAEs and UADEs, confirm/verify the patient's understanding of the PBLAC diary completion instructions (retrain if necessary) and issue PBLAC diary and sanitary supplies.

Schedule the SOC 24-hour follow-up phone contact and Week 2 post-treatment follow-up visit prior to discharging the subject.

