14.1.3 Anticipated Adverse Device Effects Associated with Endometrial Ablation

With all endometrial ablation procedures, serious injury or death can occur. The following adverse effects could occur or have been reported in other EA studies and may occur when the Minitouch System is used. The listing includes potential risks/effects associated with administration of anesthesia.

Table 14-1: Anticipated Adverse Device Effects of Endometrial Ablation

More Commonly Reported Device/Procedural and/or Post-Procedural Complications (occurs in 20 or more patients out of 100)

- Cramping or pelvic pain
- Nausea and vomiting
- Vaginal bleeding or spotting
- Vaginal discharge and/or unpleasant vaginal smell or burning or other abnormal sensation

Other Common Possible Adverse Device Effects (occurs in 20 or less patients out of 100)

- Abdominal pain or bloating
- Adhesions
- Backache
- Cervical stenosis
- Chills
- Constipation
- Diarrhea
- Fever
- Headache
- Hematometra (collection of blood in the uterus)
- Lightheadedness or fainting
- Menometrorrhagia (abnormally heavy, prolonged and irregular uterine bleeding)
- Post-ablation tubal sterilization syndrome (PATSS)
- Skin rash and/or itching burning sensation
- Weakness, fatigue, sleepiness, lack of concentration, dizziness

Rare Adverse Device Effects (occurs in 5 or less patients out of 100)

- Agitation
- Air embolism (blood vessel blockage caused by an air bubble)
- Cardiac complications
- Cervical or vaginal laceration or tear
- Complications leading to serious injury or death
- Difficulty with defecation or micturition
- Dyspareunia (painful intercourse)
- Dysuria (painful urination)
- Endometritis or Endomyometritis (inflammation of the uterine tissue)
- Hemorrhage (excessive bleeding)
- Hydrosalpinx (blocked fallopian tubes filled with fluid)
- Infection or sepsis
- Pelvic inflammatory disease (PID)
- Pregnancy-related complications
- Tissue injury (thermal, mechanical or electrical)
- Uterine necrosis (uterine tissue death due to lack of blood supply)

Page 42 of 65

- Uterine perforation (hole in the uterus)
- Vulvar pruritis (itchiness of the vulva)

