17.1.1 Intent-to-Treat (ITT) Cohort

All patients who are enrolled in the study (enrollment defined as patients who met all study eligibility criteria and in whom the procedure is initiated) are included in the Intent-to-Treat (ITT) cohort.

The ITT cohort will be used for the following analyses (as defined in Section 9.1 & 9.2):

- Primary safety and effectiveness analyses at 12-month follow-up visits.
- Safety & effectiveness analyses at 24, and 36-month follow-up visits.

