¹¹ Conduct urine pregnancy tests as needed during follow-up; conduct STD tests as needed.

¹² Special attention should be paid to medication review of contraception since patient must have been on said method for \geq 3 months prior to enrollment and must remain on the same hormonal regimen through the 12-month follow-up visit.

May not be reproduced, disclosed, or used in any form or by any means without written permission of an authorized representative of MicroCube, LLC. Hardcopies for reference only.

| Table 23-1: Schedule of Events | | | | | | | | |
|--|-------------------------|-------------------------|----------------------------|----------|-----------|-----------|-----------|-------------------|
| Assessments ² | Screening / Baseline | Procedure/ Discharge | SOC 24- hour contact | Week 2 | Month 3 | Month 6 | Month 12 | Months 24 & 36 |
| Validity Windows | Various ³ | Day 0 | 18-48 hours | ± 7 days | ± 2 weeks | ± 2 weeks | ± 4 weeks | ± 8 weeks |
| Patient PBLAC Training ¹³ | х | х | | | | | | |
| Screening PBLAC ¹⁴ | х | | | | | | | |
| Distribute PBLAC Diary and Product ¹⁵ | х | х | | х | х | х | | |
| PBLAC Diary Collection | х | | | | х | х | х | |
| Final Eligibility Assessment ¹⁶ | | х | | | | | | |
| Menorrhagia Impact Questionnaire | х | | | | х | х | х | х |
| Dysmenorrhea-related pain | Х | | | | Х | Х | Х | х |
| Procedure-related pelvic pain ¹⁷ | | х | х | | | | | |
| Patient Global Evaluation (PGE) | | | | | х | х | х | х |
| Investigator Global Evaluation (IGE) | | | | | х | х | х | х |
| AE / SAE / UADE ¹⁸ | | х | х | Х | х | х | Х | х |

¹⁶ Eligibility criteria will be assessed at baseline and reconfirmed prior to procedure initiation. Only patients who meet all eligibility criteria at that time will be included.

¹⁷ Pelvic pain (utilizing the NRS) will be evaluated BEFORE (prior to administration of procedure meds) and AFTER the procedure at discharge and during the SOC 24-hour telephone contact).

¹⁸ AE / UADE / SAE collection starts after subject is enrolled (on the day of the Minitouch procedure).

Page 60 of 65

CONFIDENTIAL & PROPRIETARY

Page 61 of 65

CONFIDENTIAL & PROPRIETARY

Page 62 of 65

CONFIDENTIAL & PROPRIETARY

| ATTACHMENT B: | SAMPLE MENORRHAGIA | IMPACT QUEST | IONNAIRE (MIQ) |
|---------------|--------------------|--------------|----------------|
|---------------|--------------------|--------------|----------------|

| MIQ concept | MIQ item | | Response scale |

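### The primary safety rate is limited to women in whom the procedure is initiated, so a serious Day 0 event that stops the case before treatment can be left out of it

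*Combined protocol and SAP*

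**What the plan says.** **Endpoint.** Section 9.2 makes the primary safety endpoint the incidence of device- or procedure-related SAEs at 12 months and expects procedure-related SAEs in fewer than 1% of women. Table 14-1 names uterine perforation among the anticipated effects, and 14.1.3 adds: "The listing includes potential risks/effects associated with administration of anesthesia".

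**Cohort.** Section 17.1.1 assigns to the ITT cohort the "Primary safety and effectiveness analyses at 12-month follow-up visits". ITT is the enrolled set, with "enrollment defined as patients who met all study eligibility criteria and in whom the procedure is initiated".

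**Eligibility.** Among the anatomy exclusions in 11.3.2, criterion 20 reads in part: "Abnormal or obstructed, or perforated cavity as determined by investigator".

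**Women not treated.** Section 12.3.3 says that consented candidates "who terminate from the study prior to treatment initiation are defined as screen failures". Section 11.9 puts any consented woman who does not go on to treatment, whatever the reason, in a consented-enrolled category. The treated-enrolled category is kept for women in whom the procedure is initiated.

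**Order on Day 0.** The suggested order in 12.4.2 has anesthesia as step 5 and Minitouch treatment as step 6. Section 9.3 records the need for cervical dilation as a procedure parameter.

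**Start of AE collection.** Section 13.7 and Table 23-1 footnote 18 tie it to enrollment; the footnote reads: "AE / UADE / SAE collection starts after subject is enrolled (on the day of the Minitouch procedure". Section 12.4.1 sets enrollment earlier than 17.1.1 does: "Once the final eligibility is confirmed, the patient is enrolled and may proceed to treatment".

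**The concern.** The endpoint covers harm from the procedure as well as from the device, but the cohort it is computed on is defined by reaching initiation. Some procedure harm can occur before the step labelled treatment: a serious reaction to anesthesia, for example, or an injury from dilation or sounding. If that harm is what stops the case, the event itself can remove the woman from the cohort meant to count it. The omission runs in one direction, because it can only lower the reported rate.

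The two enrollment definitions add a second weakness. A site that follows 12.4.1 starts AE collection at eligibility confirmation, before anesthesia. A site that takes enrollment from 17.1.1 starts it at initiation. Both are following protocol text, yet they could handle the same event differently.

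What is at stake is the primary safety estimate and its interval. The effectiveness comparison with the OPC is not involved.

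**Working it through.** **Planned denominator.** Section 17.2.1 uses a one-sample Z test with null variance, p0 = 0.66, p1 = 0.78, one-sided alpha 0.025 and 80% power:

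n = [1.960 × √(0.66 × 0.34) + 0.842 × √(0.78 × 0.22)]² / 0.12² = 113.26, rounded up to 114. This reproduces the plan.

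For 10% dropout, 114 × 1.1 = 125.4, giving the stated 126 (114 / 0.9 = 126.7 would give 127; the difference is immaterial here). I use 126 as the planned ITT size.

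**Tracing one woman through the rules.** Suppose eligibility is confirmed on Day 0, anesthesia is given, a serious event follows, and Minitouch treatment does not take place.

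| Question | Section | Answer |
|---|---|---|
| Enrolled? | 12.4.1 | Yes, at eligibility confirmation |
| Enrolled for analysis? | 17.1.1 | Only if the procedure counts as initiated |
| Category | 11.9 | Consented-enrolled if she is taken not to have proceeded to treatment |
| Screen failure? | 12.3.3 | Yes, if she ends participation before treatment initiation |
| Event collected? | 13.7, footnote 18 | Yes under 12.4.1; unclear under 17.1.1 |
| Event tabulated? | 17.5 | Yes, if reported |
| In the primary safety rate? | 17.1.1 | No, unless anesthesia counts as initiation |

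The last row turns on a term the document does not define. Collection and tabulation do not settle it, because the primary rate has its own cohort.

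**Expected count.** At a rate below 1%, 126 women give fewer than 126 × 0.01 = 1.26 events.

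**Effect of one omitted event.** Because the woman leaves both numerator and denominator, the matching comparison is 0/126 against 1/127. The exact (Clopper-Pearson) method is my choice; 17.5 asks for 95% intervals without naming one.

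- Omitted: 0/126 = 0%. Upper limit = 1 − 0.025^(1/126) = 2.9%.
- Counted: 1/127 = 0.79%. Lower limit = 1 − 0.975^(1/127) = 0.02%; upper limit = 97.5th percentile of Beta(2, 126) = 4.3%.
- With one event already in ITT, adding one woman with one event takes 1/126 = 0.79% (0.02% to 4.3%) to 2/127 = 1.57% (0.19% to 5.6%).

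These counts are illustrative. The documents do not say how often such events occur before initiation.

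**The case against.** The strongest reply is that the procedure may already count as initiated once anesthesia begins. Anesthesia is described in 13.16.3, inside the section on the Minitouch procedure; 9.3 lists anesthesia regimen and cervical dilation under the procedure heading; and step 6 of 12.4.2 can be read as one part of a longer procedure, in an order that is only suggested. On that reading the woman is in ITT and her event is counted. This stands as a possible reading, so the event can escape the rate but does not certainly do so. It is not the only reading: 12.3.3 speaks of treatment initiation, 11.9 turns on proceeding to treatment, and 12.4.2 separates the two steps.

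A reader might also infer that such an event would go unrecorded. The documents do not support that as the normal course. Under 12.4.1 and 13.7 collection starts before anesthesia, serious events go to the sponsor within 24 hours (14.3), the CEC adjudicates safety (section 15) and reported events are tabulated (17.5). The remaining doubt comes only from the competing definition in 17.1.1.

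A third inference is that exclusion 20 turns a procedural perforation into a screening outcome. Read in full, it covers "Abnormal or obstructed, or perforated cavity as determined by investigator via standard clinical practices", with hysteroscopy and saline sonohysterography as examples, and it sits under patient anatomy beside congenital malformations and polyps. Cavity integrity is not among the Day 0 rechecks named in 12.4.1, and 11.8.1 treats an exclusion discovered after enrollment as a protocol deviation, not a termination. Although 12.4.2 and footnote 16 call for a general eligibility review before initiation, exclusion 20 is not the source of the gap and has no bearing on anesthesia events. What stands is that 11.8.1 fits poorly with the requirement in 17.1.1 that all eligibility criteria were met.

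Finally, detail may sit in the CEC charter or the Instructions for Use, which are not part of the document reviewed. Cohort membership for a primary endpoint should still be readable from the analysis section.

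**Conclusion.** The concern holds as a gap in 17.1.1, read with 11.9, 12.3.3, 12.4.1, 12.4.2, 13.7 and footnote 18. A serious, procedure-related Day 0 event that stops the case before treatment can be left out of the primary safety rate, and no rule says how such an event enters it. The conclusion assumes that initiation is not defined elsewhere in a way that includes anesthesia and instrumentation.

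The absolute effect is small: one event moves the estimate between 0% and about 0.8%, and the upper limit between 2.9% and 4.3%. With fewer than about 1.3 events expected, however, one counting rule can decide whether the headline rate is zero. Neither 9.2 nor 17.4 sets a performance goal or a test for safety, so the reported estimate is affected and no pass/fail decision changes. The documents do not support a claim that such events have been or will be missed.

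**What to change.** 1. In 17.1.1 and 17.4, define the primary safety cohort as all women who receive the first Day 0 procedure medication, anesthesia or uterine instrumentation, whether or not Minitouch treatment follows. Safety counting then no longer depends on the undefined term.
2. In 13.7 and footnote 18, state that AE/SAE/UADE collection starts at Day 0 eligibility confirmation, as 12.4.1 implies, and continues for women who are then not treated. Tying collection to the later cohort-entry point would risk narrowing what is collected now. Align the enrollment wording in 11.9, 12.4.1 and 17.1.1.
3. In 12.3.3, state that Day 0 events in women not treated are reported and sent to the CEC, which rules on relatedness in the usual way. The text should not fix that ruling in advance.

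The effectiveness ITT cohort is unchanged, and so are decisions on whether a woman is treated; these edits concern counting only. The cost is protocol and SAP wording plus AE forms for the few women prepared but not treated. The downside for the sponsor is that the reported SAE rate may be slightly less favourable.
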